2.8.1 Adverse events (AEs)

An adverse event (AE) is any untoward medical occurrence (i.e., any unfavorable and unintended sign [including abnormal laboratory findings], symptom or disease) in a patient or clinical investigation of a patient after providing written informed consent for participation in the study. That means that a patient can report AEs before having started study medication. For reporting purposes, the main focus will be on treatment emergent adverse event (TEAE), defined as any adverse event which started on or after the day of first dose of study medication.

Except for serious TEAEs and death, only TEAEs up to and including safety cut-off of 100 days after last administration of study drug will be included in the analyses. All serious TEAEs and death will be included, regardless of safety cut-off.

AEs will be reported by primary system organ class (SOC) and preferred term according to the Medical Dictionary for Regulatory Activities (MedDRA). The MedDRA version used for reporting the study will be described in a footnote.

The number and percentage of patients reporting any TEAEs (referred to as incidence of any TEAEs later) will be summarized by primary SOC, preferred term and treatment. Separate summaries will be provided for serious TEAEs, drug related TEAEs, TEAEs leading to permanent discontinuation of study drug and most common TEAEs ($\geq 2\%$ in any of the treatment groups). Additionally, incidence of any TEAEs will also be summarized by SOC, preferred term, and maximum CTCAE grade. Missing CTCAE grade will not be imputed.

If a patient reported more than one adverse event within the same primary system organ class, the patient will be counted only once with the maximum CTCAE grade at the system organ class level, where applicable.

All AEs will be presented in listings.

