3.1 Study design

This is a randomized, open-label, multi-center, parallel group 12-week study to evaluate the pharmacokinetic bioequivalence of ofatumumab injected by PFS or AI devices. The study design includes four parallel groups of RMS patients. Assessment of the primary and secondary endpoints are performed based on data collected through the dosing interval between Week 8 and Week 12 where approximate steady-state pharmacokinetics are anticipated.

Randomization: A total of approximately 150 eligible patients will receive open-label ofatumumab 20 mg sc every 4 weeks (after an initial loading regimen of three weekly 20 mg doses in the first 14 days). Patients will be randomized in a 5:5:1:1 ratio into the following 4 groups dependent on what type of injection device they will use and the location of their injection (62 subjects for groups 1 and 2, and 13 subjects for groups 3 and 4). Randomization will be stratified by body weight (< 60 kg, 60-90 kg, > 90 kg) to ensure a balance between covariates with potential impact on the primary endpoint. Randomization will not be blinded as

the endpoints of the study are primarily related to pharmacokinetics and all patients will be receiving active treatment at identical dosing regimens.

- Group 1: PFS, abdomen
- Group 2: AI, abdomen
- Group 3: PFS, thigh
- Group 4: AI, thigh

Interim analyses: The study will feature one interim analysis that will be conducted when approximately 36 patients have completed Week 12 (Section 3.5).

The study has 3 Parts:

- Part 1 – Screening
- Part 2 - Treatment
- Part 3 - Safety follow-up

[figure not shown]
Part 1 – Screening

- The Screening period can last up to 30 days and consists of Screening and Baseline assessments. Patient eligibility will be determined based on the Screening and/or Baseline assessments.
- Patients may be rescreened if they do not initially meet eligibility criteria. All assessments must be repeated.

Part 2 – Treatment

Graphical outline of Part 2, Treatment period study design with four parallel groups. Evaluation of primary and secondary end-points are performed between Week 8 and Week 12.

Figure 3-1 Study design – Part 2

The study Part 2 Treatment period will consist of an initial induction phase (Week 0 to Week 4) and a pharmacokinetics phase (Week 8 to Week 12) at approximate steady-state conditions.

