- its duration (start and end dates) or if the event is ongoing an outcome of not recovered/not resolved must be reported.
- whether it constitutes a serious adverse event (SAE - See [Section 7.2.1](#) or definition of SAE) and which seriousness criteria have been met.
- action taken regarding (investigational) treatment

All adverse events must be treated appropriately. Treatment may include one or more of the following:

- no action taken (eg further observation only)
- study treatment interrupted/withdrawn
- concomitant medication or non-drug therapy given
- non-drug therapy given
- patient hospitalized/patient's hospitalization prolonged (see [Section 7.2.1](#) for definition of SAE)
- its outcome (not recovered/not resolved; recovered/resolved; recovering/resolving, recovered/resolved with sequelae; fatal; or unknown)

Once an adverse event is detected, it must be followed until its resolution or until it is judged to be permanent, and assessment must be made at each visit (or more frequently, if necessary) of any changes in severity, the suspected relationship to the study drug, the interventions required to treat it, and the outcome.

Information about common side effects already known about the investigational drug can be found in the Investigator Brochure (IB). This information will be included in the patient informed consent and should be discussed with the patient during the study as needed. Any new information regarding the safety profile of the medicinal product that is identified between IB updates will be communicated as appropriate, for example, via an Investigator Notification or an Aggregate Safety Finding. New information might require an update to the informed consent and has then to be discussed with the patient.

The investigator must also instruct each patient to report any new adverse event (beyond the protocol observation period) that the patient, or the patient's personal physician, believes might reasonably be related to study treatment. This information must be recorded in the investigator's

source documents; however, if the AE meets the criteria of an SAE, it must be reported to Novartis.

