7.2 Serious adverse events

7.2.1 Definition of SAE

An SAE is defined as any adverse event [appearance of (or worsening of any pre-existing)] undesirable sign(s), symptom(s) or medical conditions(s) which meets any one of the following criteria:

- is fatal or life-threatening
- results in persistent or significant disability/incapacity
- constitutes a congenital anomaly/birth defect
- requires inpatient hospitalization or prolongation of existing hospitalization, unless hospitalization is for:
 - routine treatment or monitoring of the studied indication, not associated with any deterioration in condition (specify what this includes)
 - elective or pre-planned treatment for a pre-existing condition that is unrelated to the indication under study and has not worsened since signing the informed consent
 - treatment on an emergency outpatient basis for an event not fulfilling any of the definitions of a SAE given above and not resulting in hospital admission
 - social reasons and respite care in the absence of any deterioration in the patient's general condition
- is medically significant, eg defined as an event that jeopardizes the patient or may require medical or surgical intervention.

All malignant neoplasms will be assessed as serious under "medically significant" if other seriousness criteria are not met.

Life-threatening in the context of a SAE refers to a reaction in which the patient was at risk of death at the time of the reaction; it does not refer to a reaction that hypothetically might have caused death if it were more severe (please refer to Annex IV, ICH-E2D Guideline).

Medical and scientific judgment should be exercised in deciding whether other situations should be considered serious reactions, such as important medical events that might not be immediately life threatening or result in death or hospitalization but might jeopardize the patient or might require intervention to prevent one of the other outcomes listed above. Examples of such events are intensive treatment in an emergency room or at home for allergic bronchospasm, blood dyscrasias or convulsions that do not result in hospitalization or development of dependency or abuse (please refer to Annex IV, ICH-E2D Guideline).

Any suspected transmission via a medicinal product of an infectious agent is also considered a serious adverse reaction.

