2.1 Data analysis general information

Novartis statistical and programming team will be performing the final CSR analysis as planned in this document unless otherwise specified. The Statistical Analysis System (SAS) 9.4 and/or R 15.2.1 or higher versions will be used.

Unless otherwise stated, summary tables/figures/listings will be on all patients in the respective analysis sets. Categorical data will be presented as frequencies and percentages. For continuous data, mean, standard deviations, median, 25th and 75th percentiles (optional), minimum and maximum will be presented.

The Week 12 CSR analysis cut-off date will be the Week 12 visit date or EOS date if patients drop out of the study prematurely. All data up to this date will be included in the Week 12 CSR. A complete analysis of the post-treatment safety follow-up will be provided in the Final CSR when all patients have completed Safety FU period.

For analyses of adverse events, only data up to and including the safety cutoff of 100 days (5 x 20 days takes the long half-life of ofatumumab into account) after last administration of study drug or the subject entered the Study G2399 will be considered. Therefore, observations obtained more than 100 days after last administration of study drug will be excluded from the

analyses. Nevertheless, all serious adverse events (SAE) and all deaths, regardless of the safety cut-off will be summarized.

All data (collected or derived) will be listed appropriately.

Table 2-1 provides an overview on all planned reporting.

Table 2-1 Analyses for Week 12 registration vs. Final CSR

	Week 12 registration CSR	Final CSR
PK + immunogenicity	Complete	Complete
Tables + figures of planned safety assessments ¹	Complete up to Week 12 / EOS, no reporting of assessments during safety follow-up	Complete, including all assessments during safety follow-up
Listings of planned safety assessments ²	Complete up to 12 week DBL date	Complete, including all assessments during safety follow-up
Adverse events	Up to and including the safety cutoff of 100 days after last administration of study drug or the subject entered the Study G2399 or 12 week DBL date, whatever comes first	Up to and including the safety cutoff of 100 days after last administration of study drug or the subject entered the Study G2399, whatever comes first

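### The TEAE definition uses start date alone, so a screening-onset event that worsens after dosing is counted or dropped according to how the site records it

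*SAP*

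**What the plan says.** SAP 2.8.1 makes TEAEs the main focus of adverse event reporting, a TEAE being "defined as any adverse event which started on or after the day of first dose of study medication". The tables of any, serious, drug-related, treatment-discontinuing and common TEAEs, and of maximum CTCAE grade, are built on that definition, as are the special-interest tables in SAP 2.8.1.1. Neither document adds a clause for events that worsen.

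The SAP recognises that events can precede dosing: "That means that a patient can report AEs before having started study medication". Protocol 3.1 gives the length of that window: "The Screening period can last up to 30 days and consists of Screening and Baseline assessments".

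On recording, Protocol 7.1 requires follow-up of each event to resolution or permanence, and says "assessment must be made at each visit (or more frequently, if necessary) of any changes in severity". The SAE definition in Protocol 7.2.1 opens with "appearance of (or worsening of any pre-existing" and goes on to signs, symptoms and conditions.

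On serious events the SAP has two rules. Section 2.1: "all serious adverse events (SAE) and all deaths, regardless of the safety cut-off will be summarized". Section 2.8.1: "All serious TEAEs and death will be included, regardless of safety cut-off".

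**The concern.** SAP 2.8 rests the safety assessment primarily on adverse event frequencies. A definition based on start date alone asks when the event began, not whether it got worse on treatment. Take an infection or headache that is Grade 1 in screening and reaches Grade 3, or leads to hospital admission, after injections have begun. The post-dose change is what a safety table should show, yet the start date lies before Day 1.

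The plan handles worsening in other domains. SAP 2.8.3 tabulates new or worsening laboratory abnormalities by CTC grade, and SAP 2.8.5 tabulates worsening suicidal ideation against pre-treatment history. Clinical adverse events have no equivalent. At stake are the completeness and consistency of the TEAE counts, including the serious and maximum-grade tables.

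**Working it through.** The plan gives no figure to reproduce. The check is to follow one event through the rules.

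**The event.** It starts after consent and before first dose, is ongoing on Day 1, and later rises in grade or becomes serious.

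**Case A: one continuing record.** The start date precedes Day 1, so the event fails the SAP 2.8.1 test. It is absent from the any-TEAE, serious-TEAE, maximum-grade and special-interest tables, whatever grade it reaches.

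**Case B: the worsening is entered as a new record.** The new start date is on or after Day 1. The event is a TEAE and is counted.

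**Which case do the documents prescribe?**

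- Towards A: Protocol 7.1 has changes in severity followed within an event already detected. Protocol 7.2.2 has progression of an SAE reported as follow-up to the original event, though that rule concerns events already serious.
- Towards B: Protocol 7.2.1 treats worsening of something pre-existing as capable of being an SAE in itself. SAP 2.8.1.1.3, a counting rule for the registry tables, foresees consecutive records of the same term that may differ in severity or seriousness.
- Neither document instructs sites to keep or to split the record when an event worsens.

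The same clinical course can therefore be counted in one patient and dropped in another.

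**Scope.** Only events that begin between consent and first dose are affected. Under Protocol 6.6.1, findings present before consent go to medical history, so their later worsening could be entered as an adverse event with its own start date.

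**The two rules for serious events.** A screening-onset event that becomes serious after dosing falls within SAP 2.1, which has no treatment-emergent restriction. Table 2-1 also refers simply to serious adverse events and deaths. In Case A the same event falls outside the serious-TEAE table of SAP 2.8.1. The two sections give different counts.

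**Size of one event.** With the planned arms of 62 and 13 patients (Protocol 3.1), one patient changes an incidence by:

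- 1/62 = 1.6 percentage points in an abdomen arm;
- 1/13 = 7.7 percentage points in a thigh arm.

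The common-TEAE table uses a threshold of 2% in any arm. One patient in a thigh arm (7.7%) is enough to bring a term into that table. An abdomen arm needs two (2/62 = 3.2%). These figures show the sensitivity to one patient; they do not estimate how many events are missed.

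**The case against.** The strongest answer is that the loss is conditional. Case report form completion rules are not in the documents, and if sites open a new record when grade or seriousness changes, nothing is lost. That stands. A reader might infer that every such event is missing from every table, but the text does not establish it. It also does not rescue the plan, because a count that depends on an unstated recording habit is not well defined.

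A reader might also infer that these events appear only in listings. All adverse events are listed, but that is not the only place. SAP 2.1 summarises all SAEs, the liver query tables in SAP 2.8.1.1.2 are worded for adverse events without the treatment-emergent restriction, and laboratory worsening and suicidality have their own tables.

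A third tempting reading is a bias towards good tolerability. In Case A the missing clause can only lower the counts. The definition as a whole, however, also admits events that start on Day 1 before the injection, which raises them. All four arms receive the same drug and regimen under the same rule, and nothing in the documents suggests that a device comparison is distorted.

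Nor does the length of screening measure the loss. As a share of time to Week 12 the maximum is 30/(30 + 84) = 26%. With the 100-day safety cut-off after a Week 12 injection, for a patient not entering the extension, it is 30/(30 + 84 + 100) = 14%. Both are shares of calendar time, not rates of missed events. The exclusion of active systemic infections and medically unstable conditions (Protocol 4.2) narrows the field further.

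Finally, the adverse event fields listed in Protocol 7.1 include grade, start and end dates and seriousness, but no date of grade change. A revised definition may not be derivable from every record. That stands, and the fix needs a fallback.

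**Conclusion.** The point holds in conditional form. SAP 2.8.1 omits post-dose worsening of a screening-onset event from the TEAE, serious-TEAE, maximum-grade and special-interest tables whenever the worsening stays in the original record. Protocol 7.1 suggests that it would, without settling the matter. The conflict between SAP 2.1 and 2.8.1 on serious events is present in the text regardless of recording practice.

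The number of affected events cannot be obtained from the documents. It is probably small, since it needs an event that starts in a window of at most 30 days, is still present at first dose, and then worsens. The pharmacokinetic bioequivalence analysis is untouched. This is a cheap improvement to the safety tables, not a flaw in the trial's main conclusion.

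**What to change.** 1. Amend SAP 2.8.1 so that a TEAE is *an adverse event that started on or after the first dose, or that was present before the first dose and increased in CTCAE grade or became serious on or after it*. Count such an event at its maximum post-dose grade.
2. State a fallback for records with no date of grade change. Either require the worsening to be entered as a new record with its own start date, or count an event ongoing at first dose as a TEAE if the date of worsening cannot be shown to precede dosing. The current SAP version is dated after a database lock, so for records already locked the second option is the practical one.
3. Reconcile SAP 2.1 with 2.8.1 so that events with onset before dosing that become serious after it are tabulated.

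The cost is a sentence or two in the SAP and a small extra derivation. The SAP has already had two addenda after database lock, so a dated clarification or a supplementary table in the Final CSR would be enough. TEAE counts may rise slightly, and the second fallback may admit a few events that in fact worsened before dosing.

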2.8.1.1 Adverse events of special interest / grouping of AEs

Selected tables will be produced for Adverse Events of Special Interest (AESI) (i.e., risks) defined in the latest version of case retrieval sheet (eCRS) at the time of analysis implementation (i.e., study database lock). Specifically, incidence of TEAEs that fulfill the risk search terms as defined in eCRS will be summarized by risk name, preferred term and treatment. Similarly, separate summaries will be provided for serious TEAEs that fulfill the risk search terms as defined in eCRS. Additionally, incidence of any TEAEs that fulfill the search terms as defined in eCRS will also be summarized by risk name, and maximum CTCAE grade.

2.8.1.1.1 Injection reaction related AEs

Incidence of injection site reaction AEs and injection systemic reaction AEs as collected in the relevant CRF pages will be reported as part of the AE summary tables as two preferred terms respectively.

Additionally, incidence of injection site reaction AEs and injection systemic reaction AEs will be reported separately for each injection.

For summaries of injection systemic reaction AEs specified in this section, reaction/symptom start date and time will be compared with the injection date and time. Only reactions/symptoms within 24 hours after injections will be included (i.e., time to onset of reaction \leq 24 hours). The time to onset of reaction will be derived as (reaction start date/time – injection date/time).

Symptoms listed in the injection site reaction or injection systemic reaction CRF pages will be summarized by providing the number and percentage of patients with each of the symptoms and pre-specified grouping of symptoms as well as overall. These summaries will be provided for each injection as well as cumulatively for all injections.

For the injection site reaction, no grouping of symptoms will be specified. For the injection systemic reaction, symptoms will be grouped under 6 categories as defined below and the number and percentage of patients with at least one symptom reported under the category will be provided for each category.

- Skin/mucosal tissue symptoms: Rash, Urticaria, Pruritus general, Flushing
- Respiratory compromise: Dyspnea, Bronchospasm, Chest discomfort, Cough
- Related to change in vital signs: Hypotension, Hypertension, Dizziness, Tachycardia
- Gastrointestinal symptoms: Nausea, Vomiting, Abdominal pain, Diarrhea
- Musculoskeletal/connective tissue symptoms: Arthralgia, Myalgia, Back pain
- Other manifestations: Fever, Headache, Chills, Asthenia, Fatigue, and Other

For the injection systemic reaction, time to onset of the first symptoms after each injection will be summarized by cumulative hour intervals (i.e., 0 to 1, 0 to 2, 0 to 3, etc. until 0 to 24 hours). These summaries will be provided for each injection as well as cumulatively for all injections.

The proportion of patients with injection site reactions and the proportion of patients with injection systemic reactions will be plotted by treatment group against the injection sequence numbers (injections 1, 2, 3, 4, 5, 6 etc.).

For the first 3 injections, additional summaries will be provided by category of injection related premedication. Specifically, 9 categories are defined as 1) no injection related premedication, 2) type 1, 3) type 2, 4) type 3, 5) type 1+ type 2, 6) type 1+ type 3, 7) type 2+ type 3, 8) type 1+ type 2+ type 3, 9) Any injection related premedication. The types 1 to 3 refer to protocol specified three types of injection related premedication as stated in [Section 2.4.2.3](#).

A separate listing for injection site reaction AEs and injection systemic reaction AEs will be provided where all reported injection related reactions (IRR) (regardless of timing) will be listed along with the corresponding injection sequence number and time to onset from the most recent injection as well as from Day 1. The listing will be sorted by injection of first occurrence of symptoms. Specifically, under the first injection, patients whose first IRR was associated with the first injection will be listed; within a patient all IRRs to all injections will be listed chronologically. Under the second injection, patients whose first IRR was associated with the second injection will be listed; similarly, within a patient all IRRs to all injections will be listed chronologically. The listing will continue with subsequent injections until all patients with IRRs are included in the listing.

